### 3 OBJECTIVES AND OUTCOME MEASURES/ENDPOINTS

The aim of this research is to feasibility test a trained peer-supported group clinic intervention for people with SMI who have increased risk of CVD.

# 3.1 Primary objective

Building on development work, evidence from a systematic review and an experience-based codesign process leading to the development of a co-produced peer-supported group clinic intervention, the objectives of this study are:

- a. To establish the feasibility of the intervention for future evaluation in a randomised controlled trial (RCT), specifically:
- Establish the feasibility of recruitment and retention strategies for the main trial
- Assess the acceptability of, and retention to the planned intervention for individuals with SMI and elevated CVD risk
- Determine the feasibility of collecting primary and secondary outcome data for the main trial
- Estimate the location (proportion) and variability (confidence intervals) of the primary outcome to refine the power calculations for the main trial
- b. To refine the content and delivery strategies for the intervention
- c. To determine the best method of evaluating intervention implementation and fidelity.

# 3.2 Secondary objectives

Not applicable for this feasibility study

# 3.3 Outcome measures/endpoints

The main outcome of this research will be a final, revised content and delivery strategies for the peersupported group clinic intervention and the best method for evaluating the intervention in a full RCT.

# 3.4 Primary endpoint/outcome

Described in the table in Section 3.6

# 3.5 Secondary endpoints/outcomes

Not applicable as this is a feasibility trial.

# 3.6 Table of endpoints/outcomes

Objectives	Outcome Measures	Timepoint(s) of evaluation of this outcome measure (if applicable)
Primary Objectives	
 
Participant recruitment & retention rate
 
Acceptability (as assessed by focus group/interview
 
Feasibility of collecting:
 
Waist and hip circumference
 
BMI
 
Triglycerides
 
HDL-cholesterol
 
LDL-cholesterol
 
Total cholesterol
 
HbA1c
 
Blood pressure
 
Questionnaires as listed in Section 7.7 (so to determine mean and standard deviation (SD) of measurements required for the future full RCT)
 
	Baseline (pre-intervention), 3 month and 6-month follow up

### 4 TRIAL DESIGN

Non-randomised mixed method feasibility study

# 5 TRIAL SETTING

This is a multi-centre study, which will be conducted at four NHS mental health Trusts with their GP surgery/integrated care systems (ICS), community healthcare NHS Trust and community/voluntary sector partners. The four sites are East London NHS Foundation Trust (ELFT), North East London NHS Foundation Trust (NELFT), Birmingham & Solihull Mental Health NHS Foundation Trust, South West London and St Georges Mental Health NHS Trust.

Participants will be recruited from community mental health services (i.e. community mental health teams, recovery teams, early intervention in psychosis services, enhanced primary care services and their equivalents at each site), in four mental health NHS Trusts in England, and GP surgeries/regional integrated care systems (ICS) in coterminous areas, as well as through community sector organisations identified in our programme equality, diversity, and inclusion (EDI) work.

### 6 PARTICIPANT ELIGIBILITY CRITERIA

### 6.1 Inclusion criteria

### Service users

Participants will:

- Be aged 18 to 75 years
- Have capacity to consent to participate in research
- Currently on the caseload of mental health services in community settings or on GP/ ICS severe mental illness (SMI) list
- Current primary diagnosis of schizophrenia-spectrum disorders (ICD-10 diagnoses F20–29) or bipolar disorder (F31) or in Early Intervention for Psychosis Services (EIPS) with formal diagnosis of psychosis (ICD-10 diagnoses of F29) or an aforementioned diagnosis.
   If on psychotropic medication, on stable dose for 90 days (N.B. This refers specifically to either adding or changing to a new antipsychotic medication, but not applies to dosage adjustment of a pre-existing antipsychotic medication.)
  - o Enhanced CVD risk as indicated byany one of:Obesity defined as: waist circumference over 102cm in men (or >90cm in non-white men) or over 88cm in women (or >80cm in non-white women) or BMI≥25 kg/m² (or ≥23 kg/m² in non-white people)
  - Hypertension defined as: blood pressure over 130/85 mmHg or documented hypertension on medication
  - Dyslipidaemia defined as: fasting triglyceride level over 1.7mmol/l or total cholesterol
     ≥5.0 mmol/L or on medication for hyperlipidaemia (e.g. statin) or high-density lipoprotein (HDL) cholesterol level less than 0.9mmol/l (men)/1mmol/l (women)
  - Hyperglycaemia defined as: HbA1c > 37 mmol/mol (5.5%) or fasting plasma glucose level ≥5.6 mmol/l or documented Type-2 diabetes (T2D)
- If on treatment for T2D, hypertension or hyperlipidaemia, on stable dose medication for at least 90 days

For the purposes of the feasibility study, we will adopt a purposive sampling approach to identifying participants to ensure diversity in our sample in order that we obtain feedback on the intervention from racialised and other marginalised perspectives.

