# 7.1.2 Screening

# Service user participants

Following informed consent (see 7.2) obtained from identified service users as outlined above, participants will meet a research nurse in person who will go through the eligibility criteria screening (see section 6 for the Inclusion and Exclusion criteria). Demographic data including age, sex, ethnicity, will be collected. Cardio-metabolic risk data will be confirmed by a research nurse using Standard Operating Procedures to measure each indicator as defined above and as follows:

- waist circumference
- body mass index
- blood pressure
- full fasting lipid profile (including triglyceride level, high-density cholesterol, low-density cholesterol, and total cholesterol levels)
- HbA1c
- smoking status, tobacco, and betel nut or paan (or pan as it is also called) use
- alcohol consumption
- All variables collected from primary care records or by research nurse to calculate QRISK3 scores

The following data will be extracted from clinical notes, and further checked with participants:

- current mental health diagnosis
- current co-morbid physical health conditions
- current prescribed medication

Those that are eligible (as per 6.1) will go on to complete baseline data collection (See 7.6), and to be allocated to the intervention.

People identified with uncontrolled hypertension (i.e. either Systolic BP ≥200 mmHg or a diastolic BP >115 mmHg) or suspected of familial hypercholesterolaemia will be referred to their GP and will not continue in the feasibility study. People who are not eligible for the study because they do not fulfil criteria for metabolic syndrome or for other reasons will not continue in the feasibility study. They will be provided with evidence-based healthy lifestyle information by the research nurse and encouraged to make an appointment with their GP for their next annual physical health check.

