### 7.7 Trial assessments

At baseline only, we will collect participants' sociodemographic data and QRISK3. At baseline, 3-month and 6-month time points, participants will complete further psychometric, anthropometric measures, blood tests, and self-completed assessments, as follows:

- Psychiatric symptoms using the Modified Colorado Symptom index
- · Lifestyle behaviour, measured using:
  - o Diet Dietary Instrument for Nutrition Education (DINE)(49), adapted by IMPaCT(50)
  - o International Physical Activity Questionnaire Short Form (IPAQ-SF)(51)
  - Cigarette smoking, tobacco and betel nut or paan (also spelled as pan) use smoking/paan/pan use status and number smoked per day; number of paans chewed per week
  - Alcohol Alcohol consumption test (AUDIT-C)
- Health-related quality of life measured using the EQ5D-5L
- Depression measured using the PHQ9
- Self-efficacy measured using the Generalised Self Efficacy scale
- Social network measured using the Lubben Social Network Scale
- Therapeutic relationship measured using the STAR
- Progress towards achievement of personalised lifestyle goals, measured with the Goal-based outcome tool
- DIAMONDS Service Use Survey

Service user participants will also be asked to wear a wrist-worn accelerometer for one-week periods prior to the start and in months 3 and 6 of the intervention.

The following data on recruitment, questionnaire completion and intervention attendance will be collected during the intervention period:

- Number of participants screened
- Number with possible presence of metabolic syndrome and invited to participate in study
- Number confirmed as eligible after initial clinical assessment and invited to continue to take part in intervention
- Reason for declining participation where applicable
- Intervention session attendance
- Follow-up data completion rate (questionnaires and clinical data)
- Reason for dropout where applicable

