- c. Three one-to-one peer support sessions per participant, bringing experiential knowledge, role modelling and social connection work. Members of this team have piloted a modified, peer-supported version of an established wellbeing mapping intervention, designed to enable and empower connection to people, places and activities that are supportive of each individual in a personalised approach to adopting a more healthy lifestyle;
- d. Strategies to build and maintain peer-to-peer support between group clinic members outside of clinic meetings, such as further in-person meetings/drop-in groups utilising local resources (e.g. Park Walk) or a social media group delivered via Whatsapp or closed Facebook group (operated in accordance with participating NHS Trust's policy) offering fortnightly motivating messages with tips;
- e. Monitoring impact of psychotropic medication on cardiovascular risk (e.g. weight gain) with engaging with GP/ psychiatrist to review/ change medication as indicated;
- f. Signposting to annual health checks, follow-up with GP for shared care plan consultation and referral to treatment and signposting to community-based support as appropriate; and
- g. Group booster session at three months post-clinic to monitor and feedback on maintenance of behaviours/ provide refresher psychoeducation.

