# 10.3 Statistical analysis plan

As this is a feasibility study, there will be no formal hypothesis testing, however the analysis plan for all measures collected is summarised below:

Quantitative data will be analysed using STATA. No formal hypothesis testing will be performed. Categorical data will be presented as counts and percentages and continuous outcomes as mean and standard deviation (or median and IQR as appropriate). Corresponding 95% confidence intervals will be calculated for estimates to refine trial parameters as necessary.

Reversal of metabolic syndrome at end of intervention is likely to be the primary outcome used within the future full trial. The proportion of participants with a reversal of metabolic syndrome and/or reduced severity of metabolic syndrome will be estimated, alongside measures of variability (i.e. confidence intervals). Estimates will be used to feed into the design of the definitive trial where appropriate, because they may lack precision and may need to be inflated.

Transcripts of qualitative data - interviews and focus groups - will be uploaded to NVivo software for analysis. Rapid framework analysis will be conducted using the intervention logic model, and Theoretical Domains Framework and Normalisation Process Technique domains, to identify areas for improvement in intervention delivery.

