## 16. APPENDICES

Appendix A - Schedule of procedures and data collection

		Stud	y period	
Timepoint	Enrolment	olment Baseline Post-allocation – i & Allocation delivery & researce		
Enrolment	-1 month	0 month	3 month	6 month
Informed consent	X			
Eligibility screen including socio-	Х			
economic data, medical and psychiatric				
history				
Allocation		X		
Intervention		4		
Usual care plus peer-group intervention				
Assessments				
Waist and hip circumference	Х		Χ	Х
BMI	X		Х	X
Fasting blood Triglycerides	X		X	X
Fasting blood HDL, LDL, total-	Х		X	X
cholesterol				
HbA1c	X		Χ	X
Blood pressure	X		Х	X
QRISK3		x (once only)		
Lifestyle behaviour, measured using:		X	Χ	X
DINE; IPAQ-SR; Cigarette smoking,				
tobacco and betel nut or paan use -				
smoking/paan use status and number				
smoked per day; number of paans				
chewed per week				
Alcohol use with AUDIT-C		Х	X	X
Modified Colorado Symptom Index		Х	Χ	X
EQ5D-5L		X	Χ	Х
PHQ9		X	Х	Х
Generalised Self Efficacy scale		X	Х	X
Lubben Social Network Scale		X	Χ	X
STAR		X	Χ	X
Goal-based outcome tool		X	Χ	X
DIAMONDS Service Use Survey		X	Χ	Х
Accelerometer x 1 week		X	Χ	Х
Adverse events			Χ	Х
Perceived acceptability			Χ	Х

Appendix B - Provisional logic model underpinning co-production of the peer supported group clinic intervention

Inputs	Barriers	Mechanisms	Process measures	Outcomes
Manualised self- management facilitation for participants co- delivered by peer workers and mental health nurses	Lack of belief that change is possible/ lack of motivation & skills Lack of understanding among clinicians of alternative worldviews/ interpretations of illness and healthy lifestyle	Targeted Behavioural Change Techniques; role modelling; social learning; goal setting and monitoring Strong 'patient/provider' relationship	Improved health behaviours (activity/ achievement of personalised goals relating to exercise, diet, alcohol, smoking and paan consumption)	Primary outcome Prevalence (reversal) of metabolic syndrome

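### Treatment counts towards metabolic syndrome at entry, but medication is not scheduled for collection at 3 or 6 months, so reversal cannot be scored on the entry basis

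*Protocol*

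**What the plan says.** Protocol section 6.1 defines enhanced cardiovascular risk by any one of four components. Two of them can be met by treatment. For blood pressure the rule is "Hypertension defined as: blood pressure over 130/85 mmHg or documented hypertension on medication". For lipids the alternatives include "or on medication for hyperlipidaemia (e.g. statin) or high-density lipoprotein (HDL) cholesterol level" below a cut-off. The glycaemic component is "Hyperglycaemia defined as: HbA1c > 37 mmol/mol (5.5%) or fasting plasma glucose level ≥5.6 mmol/l or documented Type-2 diabetes (T2D").

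Section 7.1.1 screens records on a similar list and calls the result possible metabolic syndrome. Section 7.1.2 describes people who fail screening as not fulfilling the criteria for metabolic syndrome. No other definition of the syndrome is given.

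At screening (7.1.2), "current prescribed medication" is taken from the clinical notes and checked with the participant. For later visits, section 7.7 states: "At baseline, 3-month and 6-month time points, participants will complete further psychometric, anthropometric measures, blood tests, and self-completed assessments, as follows". Neither the list that follows, nor the table in 3.6, nor Appendix A contains a medication item. Appendix A does schedule the "DIAMONDS Service Use Survey" at baseline, 3 and 6 months, but its content is not described.

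The intervention includes monitoring of psychotropic drugs with review or change by the GP or psychiatrist (8.1 e), and "follow-up with GP for shared care plan consultation and referral to treatment" (8.1 f).

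Section 10.3 names reversal as the likely primary outcome of the full trial and says: "The proportion of participants with a reversal of metabolic syndrome and/or reduced severity of metabolic syndrome will be estimated". Section 3.1 makes two things objectives: showing that the main trial's outcome data can be collected, and estimating its primary outcome to refine the power calculation.

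**The concern.** A reversal proportion compares each person's status at two times, and the comparison needs the same rule at both. At entry a blood pressure or lipid component is present if the value is abnormal or the person is treated. At follow-up only the value is scheduled. A normal reading at 6 months may come from lifestyle change or from a drug started in between, and the scheduled data cannot tell the two apart.

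This matters more here than in most studies because the intervention itself prompts treatment changes. The protocol also treats recent medication change as relevant: section 6.1 asks for 90 days of stable treatment before entry. After entry, no visit is scheduled to track it.

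Two objectives are at stake. The estimate passed to the main trial would have an unclear meaning. The test of whether the primary outcome data can be collected would also omit one of the inputs to that outcome.

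**Working it through.** **1. The plan's own figure.** The protocol gives no number for reversal. Its only design figure is the 14% margin of error for 85% retention (10.1). The design effect is 1 + (10 − 1) × 0.03 = 1.27 and the effective sample is 40/1.27 = 31.5. The plain normal-approximation half-width is 1.96 × √(0.85 × 0.15/31.5) = 12.5%; with a continuity correction of 0.5/31.5 it is 14.1%. The figure can be reproduced. This point uses only the 85% and the 40 from it.

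**2. Entry rule against follow-up schedule.**

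| Component | Counts at entry (6.1) | Scheduled at 3 and 6 months (3.6, 7.7, Appendix A) | Entry rule can be re-applied? |
|---|---|---|---|
| Obesity | Waist or BMI | Waist and BMI | Yes |
| Hypertension | Reading, or documented and on medication | Reading | No: treatment missing |
| Dyslipidaemia | Triglycerides, total cholesterol, HDL, or lipid drug | Lipid profile | No: treatment missing |
| Hyperglycaemia | HbA1c, fasting plasma glucose, or documented type 2 diabetes | HbA1c | In part |

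Fasting plasma glucose is also missing from the screening measurements in 7.1.2 and the record-screening list in 7.1.1. This is minor. HbA1c is repeated at both follow-ups, so only someone who entered on a recorded glucose with HbA1c at or below 37 mmol/mol is exposed.

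**3. Three hypothetical participants.**
- *Started.* Blood pressure is 150/95 untreated at entry; a drug is started; it is 125/80 at 6 months. The component is present by the rule in 6.1 and absent on the scheduled data. It could be scored as reversed.
- *Stopped.* Lipid component met only through a drug at entry; the drug is stopped; lipids stay normal. The component is absent by the rule in 6.1. If screening medication were carried forward it would be scored as present. The error runs the other way.
- *Not decisive.* As in the first case, but BMI stays at or above 25 (or 23 in non-white people). Under the any-one rule the person is positive either way and is not misclassified.

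**4. Size, by assumption only.** Retained: 0.85 × 40 = 34. One person is 1/34 = 2.9 points. Let r be the true reversal proportion and q the share of non-reversers whose deciding component is normalised by a new drug and scored as reversed. If only measured values are scored, the apparent proportion is r + (1 − r)q.

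| r (assumed) | q = 5% | q = 10% | q = 20% |
|---|---|---|---|
| 5% | 9.8% | 14.5% | 24.0% |
| 10% | 14.5% | 19.0% | 28.0% |
| 20% | 24.0% | 28.0% | 36.0% |

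For scale, at r = 10% the sampling half-width is about 1.96 × √(0.10 × 0.90 × 1.225/34) = 11 points, with design effect 1 + (8.5 − 1) × 0.03 = 1.225. The planned confidence interval would not reflect this misclassification. The protocol supplies neither r nor q, and the table covers one direction of error only.

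**The case against.** **The scoring rule may be in an SAP that is not shown.** True, and the absence of a rule here is not the point. A rule cannot use data that no visit is scheduled to collect.

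**Treatment at entry can be carried forward.** This stands for people already treated, and for documented diabetes. It does not cover drugs started, stopped or switched afterwards.

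**The service-use survey may record medication.** It may. Its content is not given, and nothing in the protocol assigns it that role.

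**Section 6.1 is an eligibility rule, not an outcome definition.** Formally so. But 7.1.1 and 7.1.2 call such criteria metabolic syndrome, and the protocol offers no other definition.

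**Improvement through newly prescribed treatment may be a genuine intervention effect.** This stands. Referral and medication review are parts of the intervention, so whether a drug-normalised component counts as present is partly a choice of estimand. Either choice needs the medication data.

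**This is a single-arm feasibility study without hypothesis tests.** Section 10.3 already warns that estimates may be imprecise and need inflating. That addresses sampling error, not a change of definition between visits.

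**A stronger reading is tempting:** that drug-controlled components will be scored as reversed, pushing the proportion up by 6 to 21 points (2 to 7 of 34, if 5% to 20% are affected). The documents do not support it. No scoring rule is stated, stopped drugs can push the other way, the 5% to 20% is assumed, and that sum treats every altered component as a reversed syndrome.

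**Conclusion.** The point holds as a gap in data collection. Medication decides two of the four components at entry and is not scheduled at either follow-up, while the intervention can change it. The reversal proportion therefore cannot be scored on the entry basis, nor can improvement under new treatment be separated from improvement without it.

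The size and net direction of the error cannot be computed from the protocol. What can be said is 2.9 points per misclassified person if 34 are retained, and that a person is misclassified only when the affected component decides their status. This conclusion assumes that the service-use survey does not already capture the relevant drugs with dates. If it does, the remaining need is to say so and to state the scoring rule. The fasting-glucose mismatch is real but marginal.

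**What to change.** - **Collect.** Add current antihypertensive, lipid-lowering, glucose-lowering and psychotropic medication, with start and change dates, to the 3- and 6-month CRF and to Appendix A. The source is the clinical notes already used at screening. For visits already past, the same records may allow retrospective extraction if consent and approvals cover it.
- **Score.** State in 10.3 that each component is scored by the same rule at entry and at follow-up.
- **Report both versions.** Give the reversal proportion with newly treated components counted as present, and again on measured values alone, with the number of newly treated people. This leaves the estimand open for the main trial and shows how much it matters.
- **Glucose.** For the reversal outcome, use HbA1c plus documented type 2 diabetes at every visit, so that no component rests on a measure the study does not take.

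The cost is about one CRF page per follow-up visit, filled from records, plus a short addition to 10.3. The reversal proportion may look less favourable under the first version.

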### Intervention staff

Participants will be peer (support) workers and registered mental health nurses (or other healthcare professionals or practitioners with appropriate training) who have been trained and engaged by their

employing organisation (i.e. one of the four sites) to deliver (co-facilitate) the PEGASUS intervention for the purposes of this study.

Where possible we will attempt to recruit at least one peer worker and/or nurse to the intervention team at each site who share similar heritage to racialised communities who make up a substantial proportion of the population locally (e.g. the Bengali/ Bangladeshi community in Tower Hamlets in East London).

#### 6.2 Exclusion criteria

### Service users

People who:

- Are currently admitted to acute psychiatric care (i.e. inpatient admission or current referral to a Crisis & Home Treatment Team)
- Have a primary diagnosis of alcohol or substance misuse
- Are awaiting/going through assessment with EIPS but without formal diagnosis
- Have a diagnosis of an organic mental health disorder (e.g. dementia)
- Are currently in receipt of a highly structured and/ or multi-goal healthy lifestyle intervention
   (e.g. an intervention that combines structured diet and exercise goals, or a highly structured
   research-based intervention such as DIAMONDS or PRIMROSE-A). Note: referral to single
   goal lifestyle support, as typically provided in the voluntary-sector or as online NHS advice, is
   considered as part of care as usual and will be assessed in both trial groups (see secondary
   outcomes below)
- Blood pressure or hyperlipidaemia managed outside of primary care
- Type 1 diabetes

